## **6.5.** Prior Prostate Cancer Therapies and Surgeries

For prior prostate cancer therapies, each line of therapy is captured into a group ranging from A-O, where A is the first line of therapy and O is the last line of therapy. The drugs within each are collected. Prior to locking the database, these drugs will be categorized into groups. An additional categorization will also be performed to show types of prostate cancer therapies. These therapies will be summarized overall for the drugs within the different lines of therapies. The number of therapy regimens received, and types of prostate cancer therapies will be summarized.

Progenics Pharmaceuticals, Inc. Statistical Analysis Plan – Protocol PyL-2301

September 5, 2018

Radiation therapy will be presented to show whether it was prostate related or not, and radiated site.

Months since last reported surgery will also be summarized. Surgeries will also be presented by system organ class and preferred term.

All prior prostate cancer therapies and surgeries will be presented for the safety set, the evaluable set and the per protocol set.

## 6.6. Prior Medication History and Medications Present at Entry

Prior medications will be summarized by ATC4 class and generic name using frequencies and percentages. Prior medications will also be listed.

Prior medication history will be presented for the safety set, the evaluable set and the per protocol set.

## 6.7. Conventional Imaging at Baseline

Type of bone scans, bone scans obtained within 10 hours of dosing, MRI/CT performed, and type of MRI/CT will be summarized by the safety set, the evaluable set and the per protocol set.

#### 7. EFFICACY

#### 7.1. General Considerations

Statistical tests and their corresponding confidence intervals will be two-sided at the 0.05 significance level.

The estimation of sensitivity and specificity rely on the central imaging core lab independent readers. Each reader's assessments will be summarized separately.

## 7.2. Testing Statistical Assumptions Including Comparability at Baseline

#### 7.2.1. Test of Proportions

The assumption underlying the normal approximation to the binomial distribution, used in the computation of confidence intervals for sensitivity, specificity, PPV, and NPV, is that the sample size is such that np>5 and n(1-p)>5, where n is the sample size and p is the binomial probability. It is expected that the sample size for each statistic will be sufficient to meet this assumption. In the event that the sample size is not sufficient, Agresti-Coull exact tests will be used. As there is only one treatment in this study, there will be no testing of baseline comparability.

#### 7.2.2. Test of means

The assumption of normality of the data may be violated when testing for differences in means. If data fail the Shapiro-Wilk test for normality within each group, then a Wilcoxon rank sum test will be used for the comparison of 2 groups and a Kruskal-Wallis test for comparison of 3 groups to test for differences in the distribution between groups. For 2 group comparisons, an exact 95% confidence interval will be generated for the difference scores. For a 1-way repeated

measures ANOVA, if the assumption of normality is not met then a Friedman test will be performed.

### 7.3. Statement of the Null and Alternate Hypotheses

The null and alternative hypotheses are stated in Section 4.3.

## 7.4. Subgroup Analyses

No subgroup analyses are planned, but they may be examined for exploratory purposes.

## 7.5. Multiple Comparisons and Multiplicity

Within Cohort A, the type I error rate will be preserved by requiring that both null hypotheses be rejected in order to draw the conclusion that F-DCFPyL is efficacious for imaging. In addition, the three readers from the central imaging core laboratory are independent and requiring that the same 2 of 3 readers agree about sensitivity and specificity (Cohort A) will control for type I error.

## 7.6. Analysis of the Primary Efficacy Endpoint

### 7.6.1. Primary Efficacy Analysis of Primary Endpoints

The primary analysis for subjects in Cohort A will be addressed by computing point estimates and 95% two-sided confidence intervals (CIs) for specificity first and if the null hypothesis is rejected for specificity then sensitivity will be tested next. Both outcomes are assessed on the subject level (one overall outcome per subject) in the *evaluable set*. If the *per protocol* set exists, then this analysis will be performed on the *per protocol* set as a supplemental analysis. The normal approximation to the binomial distribution is planned assuming the assumptions have been met (See Section 7.2). Sensitivity and specificity will be computed for each of three central imaging core lab independent PET/CT readers.

The null hypothesis for specificity will be rejected if the lower limit of the 95% CI exceeds 80% for at least two of the three independent central PET/CT readers. If statistical significance is achieved for specificity where the null hypothesis is rejected, then sensitivity will be tested where the null hypothesis will be rejected if the lower limit of the 95% CI exceeds 40% for the same two readers who rejected the null hypothesis for specificity.

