## 4.3. Sample Size

The primary analysis in Cohort A will test the co-primary endpoints of sensitivity and specificity of F-DCFPyL PET imaging relative to histopathology for the evaluable set of subjects in Cohort A with metastatic disease. For each co-primary endpoint, there will be three independent imaging readers. At least two of the three readers must reject the null hypothesis for specificity to be deemed a success. If specificity is a success, then the same two readers need to reject the null hypothesis for sensitivity leading to overall success of the primary endpoint. The null hypotheses will be tested in the following order:

- 1. Specificity of F-DCFPyL PET imaging relative to histopathology in Cohort A  $H_0$ :  $\pi_{Sp} = 0.80$  versus  $H_1$ :  $\pi_{Sp} \neq 0.80$
- 2. Sensitivity of F-DCFPyL PET/CT imaging relative to histopathology in Cohort A  $H_{01}$ :  $\pi_{Se} = 0.40$  versus  $H_{11}$ :  $\pi_{Se} \neq 0.40$

where  $\pi_{Se}$  is the true sensitivity and  $\pi_{Sp}$  is the true specificity of F-DCFPyL PET imaging.

A total of 262 subjects from Cohort A will provide 80% power to reject the null hypothesis about sensitivity at the 5% significance level if the true sensitivity is at least 60% and at least 80% power to reject the null hypothesis about specificity at the 5% significance level if the true specificity is at least 87.8%. These calculations are based on the following assumptions:

• the probability of a positive histopathology sample in Cohort A is 20%,

The sample size is based on the normal approximation to the binomial distribution without a continuity correction.

$$n \ge \left\{ \frac{z_{\alpha/2} \sqrt{P_0(1 - P_0)} + z_{\beta} \sqrt{P_1(1 - P_1)}}{P_1 - P_0} \right\}^2$$

where P0 are P1 are values of sensitivity under the null and alternative hypotheses, respectively. After adjusting sensitivity and specificity separately by their corresponding prevalence values, a total in 236 subjects are needed. Assuming a 10% drop out or non-evaluable rate increases the required number of subjects in Cohort A to 262.

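### The interval that decides the primary endpoints is not named; read as Wald, it gives specificity an upper-tail error of about 3.8% per reader rather than 2.5% and does not match the test used for sizing

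*SAP*

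**What the plan says.** SAP 7.1 sets the level: "Statistical tests and their corresponding confidence intervals will be two-sided at the 0.05 significance level". SAP 7.6.1 then gives the rule. For specificity, "The null hypothesis for specificity will be rejected if the lower limit of the 95% CI exceeds 80" per cent for at least two of the three readers. For sensitivity, "the null hypothesis will be rejected if the lower limit of the 95% CI exceeds 40% for the same two readers" who passed specificity. The method is described in one sentence: "The normal approximation to the binomial distribution is planned assuming the assumptions have been met". Protocol 12.5.2.1 also refers only to the normal approximation.

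SAP 7.2.1 adds a condition on that approximation, which "is that the sample size is such that np>5 and n(1-p)>5", and a fallback: "In the event that the sample size is not sufficient, Agresti-Coull exact tests will be used". The protocol contains neither, and SAP section 10 does not list them among the changes from the protocol.

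SAP 4.3 and Protocol 12.1 describe the sizing: "The sample size is based on the normal approximation to the binomial distribution without a continuity correction". The formula printed there multiplies the alpha quantile by the square root of P0(1−P0), the variance under the null. Neither document says whether the analysis interval takes its variance at the estimate (Wald) or at the null (score, that is Wilson).

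**The concern.** Two programmers could follow SAP 7.6.1 faithfully and reach different primary conclusions from the same data. A confidence interval by normal approximation, guarded by an np check and backed by Agresti-Coull, is how a Wald interval is usually described, so Wald is the likely outcome.

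That choice matters for specificity. When the true proportion is near 0.80, an estimate that happens to be high also has a smaller estimated standard error. The Wald lower limit then clears 0.80 more often than a 2.5% tail allows. It would also mean that the trial was sized for one test and analysed with another. At stake is the calibration of the rule that declares the primary endpoints met.

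**Working it through.** **Inputs.** Two-sided 5% (SAP 7.1), so 2.5% in the tail that counts as success. Nulls are 0.80 and 0.40, alternatives 0.878 and 0.60, and 20% of subjects have positive histopathology (SAP 4.3). There are 236 evaluable subjects (Protocol 12.1). This gives about 236 × 0.8 ≈ 189 node-negative and 236 × 0.2 ≈ 47 node-positive subjects.

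**Reproducing the plan's sample size.** n = {[1.96√(P0(1−P0)) + 0.8416√(P1(1−P1))]/(P1−P0)}²
- Sensitivity, 0.40 vs 0.60: 47.09; /0.20 = 235.5, so 236.
- Specificity, 0.80 vs 0.878: 184.5; /0.80 = 230.6, so 231.
- Sensitivity drives the size; 236/0.9 = 262.2, stated as 262.

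The plan's figures reproduce with the null variance. With the alternative's variance in both terms, as for a Wald test, specificity would need only 138.2 node-negative subjects. For sensitivity the two versions coincide, because 0.4 × 0.6 = 0.6 × 0.4.

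**The two limits at n = 189.**
- Wald lower limit: p̂ − 1.96√(p̂(1−p̂)/n)
- Wilson lower limit: [p̂ + z²/(2n) − z√(p̂(1−p̂)/n + z²/(4n²))]/(1 + z²/n). It exceeds 0.80 exactly when (p̂ − 0.80)/√(0.80 × 0.20/n) exceeds 1.96.

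| Correct negatives | p̂ | Wald limit | Wilson limit | Exact chance of this or more at 0.80 |
|---|---|---|---|---|
| 160 | 0.8466 | 0.7952 | 0.7883 | 6.22% |
| 161 | 0.8519 | 0.8012 (pass) | 0.7942 | 4.18% |
| 162 | 0.8571 | 0.8073 (pass) | 0.8001 (pass) | 2.70% |

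**Across sample sizes.** The number of node-negative subjects is random, so the last two columns average over Binomial(236, 0.8) for specificity and Binomial(236, 0.2) positives for sensitivity. All entries are exact binomial tails for one reader.

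| | Error at planned n | Error, n = 180 to 200 | Average error | Average power |
|---|---|---|---|---|
| Specificity, Wald | 4.18% (n = 189) | 3.05–4.59% | 3.77% | 87.3% |
| Specificity, Wilson | 2.70% (n = 189) | 1.69–2.70% | 2.19% | 81.2% |
| Sensitivity, Wald | 2.41% (n = 47) | – | 2.42% | 78.4% |
| Sensitivity, Wilson | 2.41% (n = 47) | – | 2.66% | 79.6% |

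Wald exceeds 2.5% for specificity at every n from 180 to 200. For sensitivity, both methods pass at 26/47.

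**The two-of-three rule, specificity step only.** With independent readers at 3.77% each: 3 × 0.0377² × 0.9623 + 0.0377³ = 0.4%. With identical readers it stays at 3.77%. In between, the answer depends on how strongly the readers' calls on the same subject correlate, which the documents do not give. Simulating Wald at n = 189 with an assumed equal pairwise correlation gives about 2.1% at 0.5, 2.5% at 0.6 and 3.4% at 0.8; identical readers give 4.2%.

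**The case against.** **Wald is never named.** This stands. A score interval is also a normal approximation, and the sizing section uses the same phrase for a null-variance formula. A reader might infer that analysis and sizing are shown to use different tests. The documents show only that the interval is unspecified and that Wald is permitted.

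**The plan claims 5%, and 5% is kept.** This stands too. A reader might infer from 3.8% that the trial's type I error is out of control. It is not. The figure is for one reader and one endpoint. Even with identical readers, the specificity step peaks at 4.6% over 180 to 200 node-negative subjects, and success also needs the same two readers to pass sensitivity. The two-of-three error exceeds 2.5% only if reader correlation is above roughly 0.6, which is an assumption. The 2.5% benchmark follows from using one side of a two-sided 95% interval; the plan does not state it.

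**The np>5 check guards the approximation.** A reader might infer that the check is worthless because Wald limits cover poorly at proportions of 0.95 to 0.97, where np and n(1−p) still exceed 5. That does not hold for the planned procedure. If the check is applied to observed counts, as it must be in practice, low counts move to Agresti-Coull. The combined procedure then covers 97.9% at 0.95 and 99.2% at 0.97 with n = 189. The check does leave the 0.80 boundary untouched: expected counts there are about 151 and 38 (19 and 28 for sensitivity), so the fallback would not apply.

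**The practical effect is one or two subjects at the threshold.** True, but this is the primary threshold, and the correction is only wording.

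**Conclusion.** The primary decision rests on an unnamed interval. On its most natural reading, the per-reader upper-tail error for specificity averages about 3.8% instead of 2.5%. The like-for-like comparisons with Wilson are 3.8% against 2.2% on average and 4.2% against 2.7% at n = 189. Wilson's error also varies with n and is slightly above 2.5% at the planned count.

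Sensitivity is not affected: both methods are close to 2.5%. Trial-level false success remains below the stated 5%.

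These sizes assume 236 evaluable subjects and 20% positive histopathology, as planned, and a Wald reading of SAP 7.6.1. The under-specification does not depend on that reading. Calling Agresti-Coull exact is a labelling error that would not affect the primary result at the planned counts.

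**What to change.** In SAP 7.2.1, SAP 7.6.1 and Protocol 12.5.2.1, state that the primary specificity and sensitivity decisions use the lower limit of the two-sided 95% Wilson score interval. This is the test that the sample-size formula assumes, and it removes the need for the np>5 switch in the primary analysis. Where SAP 7.2.1 says "Agresti-Coull exact tests will be used", delete the word exact; do the same in SAP 7.7.2 and 7.8.

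The cost is small: a wording change and one programming option. At 189 node-negative subjects the specificity threshold moves from 161 to 162; at other counts between 180 and 200 it rises by one or two. Average per-reader specificity power falls from about 87% to 81%, still meeting the stated 80%. Average sensitivity power is about 80%, against 78% under Wald.

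An exact Clopper-Pearson interval would also hold the tail (2.0% on average for specificity, with 80.1% power), but it would cut average sensitivity power to about 74%. Wilson fits this design better.

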#### 7.6.2. Sensitivity Analyses of the Primary Endpoints

A sensitivity analysis of the primary endpoint will be performed allowing any 2 of the 3 central PET/CT readers to reject the null hypothesis for sensitivity only after specificity has been deemed a success. This analysis will require agreement of at least 2 readers, but they do not need to be the same 2 central readers to reject the null hypothesis for specificity and sensitivity. This analysis will be performed for the evaluable and per protocol sets.

## 7.7. Analysis of Secondary Efficacy Endpoints

Analysis of secondary efficacy endpoints will be conducted regardless of the outcomes of the primary analyses. Diagnostic testing and imaging detection rates will be analyzed for the evaluable set. The PK parameters will be summarized for the PK blood set.

#### 7.7.1. NPV and PPV in Cohort A

Point estimates and two-sided 95% CIs for PPV and NPV will be computed for the prostate gland and the lymph nodes in Cohort A subjects in the Evaluable Set. The normal approximation to the binomial distribution is planned assuming the assumptions have been met (See Section 7.2). PPV and NPV will be computed for each of the three central imaging core lab independent PET/CT readers.

#### 7.7.2. PPV and Sensitivity in Cohort B

Point estimates and two-sided 95% CIs for PPV and Sensitivity will be computed from the conventional guided biopsy obtained from subjects in Cohort B for the Evaluable Set. The normal approximation to the binomial distribution is planned assuming a null hypothesis of 0.5. If the assumptions are not met, then confidence intervals derived from an Agresti-Coull exact test will be used (See Section 7.2). Results will be computed for each of the three central imaging core lab independent readers.

#### 7.7.3. Detection Rates for Lesion Counts in both Cohorts Combined

For subjects in Cohort A and B combined, the sum of the lesions per tissue type and overall per subject will be summarized showing the N, mean, median, standard deviation, minimum and maximum values for each central imaging core lab reader including the reader of conventional scans. F-DCFPyL images and conventional images will be summarized separately and the mean of each reader's results from F-DCFPyL PET/CT will be compared to conventional imaging using a one-way repeated measures ANOVA. If the assumptions are not met for this test (see Section 7.2), then a Friedman's test will be performed to determine if there is a difference between any of the groups. If significant is determined from either the ANOVA or the Friedman's test, then a Dunnett's test will be performed to show where the difference exists between each reviewer and the conventional scan. A p-value and 95% confidence interval for the difference in means will be presented for each F-DCFPyL PET/CT reviewer versus conventional imaging. This analysis will be performed on the Evaluable Set.

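### SAP 7.7.3 follows either omnibus test with a mean-based Dunnett comparison but names no error term and does not handle sphericity, so the PET-minus-conventional intervals may not have their stated 95% coverage

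*SAP*

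**What the plan says.** SAP 7.7.3 covers the secondary endpoint that sets PET lesion counts against conventional imaging in both cohorts combined, on the Evaluable Set. Counts are summed per subject for four tissue types and overall. There are four columns: three PET readers and one reader of conventional scans.

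- **Main test.** Each PET reader's mean is "compared to conventional imaging using a one-way repeated measures ANOVA".
- **Fallback.** If assumptions fail, "then a Friedman's test will be performed to determine if there is a difference between any of the groups". For this model SAP 7.2.2 names one trigger only: "if the assumption of normality is not met then a Friedman test will be performed".
- **Follow-up.** If either omnibus test is significant, "then a Dunnett's test will be performed to show where the difference exists", so the same step follows whichever omnibus test was used.
- **Reporting.** "A p-value and 95% confidence interval for the difference in means will be presented for each" PET reader against conventional imaging.

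Neither section mentions sphericity, a correction for its failure, a covariance structure, or the error term behind Dunnett's test. Protocol 12.5.2.2 plans only a descriptive summary of these counts, so SAP 7.7.3 holds the only planned formal test of this endpoint.

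**The concern.** There are two linked problems.

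**The fallback does not carry through.** If normality is rejected, the rank test acts only as a gate. Every reported p-value and interval goes back to a comparison of means, and the interval does not correspond to the rank test that opened the gate. This branch is likely to be used: the data are integer counts by tissue type, and the set mixes pre-prostatectomy patients with patients who have recurrent or metastatic disease.

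**The error term is open, and the default choice suits this design poorly.** The ordinary repeated-measures error averages the variability of all six pairwise differences among the four columns. Three of those pairs are PET reader against PET reader on the same scan. The other three are PET against conventional imaging, and only these are reported. If readers of one scan agree more closely with each other than with a different modality, the pooled error is too small for every reported contrast.

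At stake is whether the intervals for PET minus conventional mean what they say. More subjects would not help, because the ratio of the assumed to the true standard error does not depend on sample size.

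**Working it through.** **Figures in the plan.** The documents give no power, SD, correlation or interval width for lesion counts. The only figure to test is the nominal 95% level. The one sample-size calculation (Protocol 12.1, SAP 4.3) supplies N, and it reproduces: sensitivity 0.40 against 0.60 needs 47.09 positives; 47.09/0.20 = 235.5, so 236 evaluable; 236/0.9 = 262.2, matching 262. For Cohort B, 115 are dosed. Assuming 10% non-evaluable there too, 115 × 0.9 = 103.5, about 104. Total: 236 + 104 = 340.

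**Step 1. Standard-error ratio.** Let V_PP be the variance of a PET-PET reader difference and V_PC that of a PET-conventional difference. Twice the pooled mean square averages the six pairwise variances:

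2 × MSE = (3 V_PP + 3 V_PC)/6 = (V_PP + V_PC)/2.

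The contrast of interest has true variance V_PC/n. With r = V_PP/V_PC,

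SE(pooled)/SE(true) = sqrt((1 + r)/2).

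The lower limit as r goes to 0 is sqrt(0.5) = 0.707, so the standard error can be understated by at most 29%.

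With equal variances, r = (1 − ρ_PP)/(1 − ρ_PC). Assumed correlations of 0.9 (PET-PET) and 0.5 (PET-conventional) give r = 0.1/0.5 = 0.2 and a ratio of sqrt(0.6) = 0.775.

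**Step 2. Coverage.** The two-sided Dunnett critical value for three comparisons at large degrees of freedom is 2.349. The effective multiplier is 2.349 × sqrt((1 + r)/2), and the three differences have mutual correlation 1 − r/2.

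| r = V_PP/V_PC | SE ratio | Per-comparison coverage | Joint coverage |
|---|---|---|---|
| 0.1 | 0.742 | 91.9% | 88.4% |
| 0.2 | 0.775 | 93.1% | 88.7% |
| 0.5 | 0.866 | 95.8% | 91.2% |
| 0.75 | 0.935 | 97.2% | 93.2% |
| 1.0 (sphericity) | 1.000 | 98.1% | 95.0% |
| 1.5 | 1.118 | 99.1% | 97.5% |

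Per-comparison coverage drops below 95% when 2.349 × sqrt((1 + r)/2) < 1.96, that is, when r is below about 0.4.

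**Step 3. Simulation** (n = 340, 8,000 runs, nine scenarios, no omnibus gate).

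- Pooled within-subject error: joint coverage 88.6% to 93.6% in the seven scenarios with V_PP < V_PC, 94.7% under sphericity, 98.0% in the one with V_PP > V_PC.
- Among those seven, overdispersed counts with close PET readers, and conventional reads finding roughly half as many lesions: r = 0.225, SE ratio 0.785, joint coverage 88.8%. With noisier readers: r = 0.75, 92.9%.
- Unpaired Dunnett: at least 99.6% in every scenario.
- Paired differences, each with its own SE and the Dunnett critical value: 94.4% to 96.8% in all nine.

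**Step 4. False claims with the omnibus gate** (normal data, n = 300, no true difference, 4,000 runs, pooled error, critical value 2.349). Probability of at least one false Dunnett claim:

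| PET-PET / PET-conventional correlation | After Friedman | After ANOVA | No gate |
|---|---|---|---|
| 0.9 / 0.5 | 3.9% | 8.4% | 11.6% |
| 0.8 / 0.5 | 3.2% | 6.2% | 9.8% |
| 0.7 / 0.5 | 2.6% | 4.4% | 7.6% |

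A repeat with PET-conventional correlation from 0.4 to 0.6 gave the same picture: below 5% throughout after Friedman, and above 5% after ANOVA except at the lowest PET-PET correlation, 0.7, combined with PET-conventional 0.5 or 0.6.

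**The case against.** A reader might infer that the plan gives intervals that are too narrow and p-values that overstate certainty, as a plain fact. The documents do not support that, for these reasons.

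- **The error term is not stated.** Too-narrow intervals follow only from the pooled within-subject error. An unpaired Dunnett test is too wide, and a model with unstructured covariance would be about right. This stands: the defect in the text is that the choice is missing. It does not rescue the plan, because neither common reading of Dunnett's test reliably gives 95%.
- **The correlations are assumed.** The documents give none for lesion counts. If V_PP exceeded V_PC, the pooled intervals would be conservative. This stands too, so the size has to be given as a range. That V_PP is smaller is reasonable for three reads of one scan, and SAP 5.5.11 expects similar results across readers, though for SUV values rather than counts.
- **The gate limits false claims.** On the Friedman path, which skewed counts make likely, familywise error stayed below 5% in the cases examined. This stands for those cases, which used normal data. It does not help the intervals.
- **Joint coverage is the harsher yardstick,** since the SAP presents one interval per reader. That is fair: per comparison, the Dunnett multiplier absorbs the shortfall until r is below about 0.4. But a Dunnett interval is chosen for its simultaneous property, so that is the property to check.
- **Non-normality has little numerical effect.** With some 340 subjects, paired mean-based intervals held close to 95% even for overdispersed counts. This stands. Returning to means after Friedman is a mismatch between test and interval; no bias from it has been shown.

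**Conclusion.** The point holds in conditional form. SAP 7.7.3 keeps a mean-based Dunnett follow-up after a rank test and leaves both the error term and sphericity unaddressed in a design where sphericity is doubtful.

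With the pooled within-subject error and V_PP/V_PC between about 0.1 and 0.75, the three nominal 95% intervals have joint coverage of about 88% to 93%. With an unpaired error they exceed 99%. The false-claim rate is the lesser issue: below 5% on the Friedman path, and about 5% to 9% on the ANOVA path over most of the assumed range (4.4% at correlations of 0.7 and 0.5). All of these sizes rest on assumed correlations and on a choice of error term that the SAP leaves open.

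It would be wrong to read this as a threat to the trial's main result. The endpoint is one of six secondary efficacy endpoints, it has no success threshold, and the primary conclusion rests only on Cohort A specificity and sensitivity. The gap should still be closed, because this is the only planned formal comparison of lesion counts between PET and conventional imaging, and a better method costs almost nothing.

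**What to change.** In SAP 7.7.3, replace the follow-up step as follows.

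1. For each PET reader, form the per-subject difference, PET count minus conventional count, and analyse it with its own standard error. A mixed model with unstructured covariance over the four columns is an acceptable alternative.
2. Adjust over the three readers, for example with the Dunnett critical value used in the check above or with Holm's method for the p-values, and state whether the intervals are simultaneous or per reader.
3. When normality fails, take both the p-value and the 95% interval for the mean difference from the same subject-level bootstrap or paired analysis. Any signed-rank test should be labelled supportive, since pairing its p-value with a mean-difference interval would recreate the rank-against-mean mismatch.
4. State whether the comparisons and intervals are reported regardless of the omnibus result.

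The cost is SAP wording and simple code, with no new data. Intervals become wider than with pooled error: by 1/0.866 = 1.15 times at r = 0.5, and by 1/0.775 = 1.29 times at r = 0.2.
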